6.1 Inclusion Criteria

For inclusion in the study patients must fulfill ALL of the following criteria:

- 6.1.1 Patient has completed the treatment phase of their Core Study.
- 6.1.2 Patient and/or parent(s)/legal representative must be willing and able to give informed consent/assent for participation in the study (see [Section 15.2](#)).
- 6.1.3 Patient and their caregiver must be willing and able (in the Investigator's opinion) to comply with all study requirements.
- 6.1.4 Patient and/or parent(s)/legal representative is willing to allow his or her primary care practitioner and consultant to be notified of participation in the study.

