APPENDIX 4 TITRATION REGIMEN

Dose Titration Regimen*		
Day	OLE IMP Dosage	Total Daily OLE IMP Dose
1	1.25 mg/kg (pm)	1.25 mg/kg
2	1.25 mg/kg bid (am/pm)	2.50 mg/kg
3	2.50 mg/kg bid (am/pm)	5.00 mg/kg
4	2.50 mg/kg bid (am/pm)	5.00 mg/kg
5	3.75 mg/kg bid (am/pm)	7.50 mg/kg
6	3.75 mg/kg bid (am/pm)	7.50 mg/kg
7	5.00 mg/kg bid (am/pm)	10.00 mg/kg
8	5.00 mg/kg bid (am/pm)	10.00 mg/kg
9	7.50 mg/kg bid (am/pm)	15.00 mg/kg
10	7.50 mg/kg bid (am/pm)	15.00 mg/kg
11	10.00 mg/kg bid (am/pm)	20.00 mg/kg
12	10.00 mg/kg bid (am/pm)	20.00 mg/kg
13	10.00 mg/kg bid (am/pm)	20.00 mg/kg
14	10.00 mg/kg bid (am/pm)	20.00 mg/kg

* It is advised that the Investigator considers monitoring hepatic function (ALT, AST, TBL and INR levels) during the titration period for patients taking AEDs that are known to be associated with hepatic injury or failure. To minimize any elevations in hepatic function markers the titration period can be extended and the dosage of a concomitant AED and/or GWP42003-P may be adjusted at the discretion of the Investigator. If there is intolerance during titration, the patient may be maintained on a dose below 10–20 mg/kg/day. A titration rate faster than recommended may be considered if there is an increase in seizures, following consultation with the GW medical monitor.

Emerging clinical data suggest that benefit may be seen in patients in the range of 10–20 mg/kg/day.

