3.1.1 Titration Period

When patients have completed the core study from which they enter this study, they may either be receiving Placebo (of varying dose), 5 mg/kg/day GWP42003-P, 10 mg/kg/day GWP42003-P or 20 mg/kg/day GWP42003-P as per their original allocation in their respective core study. Upon entering this study, patients will titrate to 20 mg/kg/day

GWP42003-P using a recommended titration schedule during the 2-week titration period to achieve a stable dose prior to entering the maintenance period.

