4.5.1 General Approach

All endpoints will be summarized on the safety analysis set, unless specified otherwise. Endpoints will be summarized by indication including an appropriate overall summary, unless specified otherwise. Each individual endpoint section also describes any further categorization of the data above that described in this section.

Throughout this section, whenever change from baseline is referenced and the endpoint is non-seizure related the baseline that is used will be the core study baseline. Please refer to Section 4.5.9 for specific rules for the choice of baseline for seizure-related endpoints.

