4.5.2 Adverse Events

All reported AEs will be classified by system organ class (SOC), preferred term and lower level term using Version 17.1 of MedDRA.

Summaries will be presented by SOC and preferred term.

A treatment emergent AE (TEAE) is defined as an AE with a start date on or after the first dose of IMP within this OLE study. If an AE has a partial start date and it is unclear from the partial date (or the stop date) whether the AE started prior to or post first dose of IMP then the AE will be considered treatment emergent. If the start date of the AE is the same as the date of first dose of IMP and the plausible relationship to study medication is marked on the CRF as "Prior to study medication" then the AE will not be considered treatment emergent.

An AE will be considered treatment-related if the plausibility relationship to study medication is recorded on the CRF as 'yes'. If the data on plausibility relationship to study medication is missing then the AE will be considered treatment-related.

An AE will be considered leading to permanent discontinuation of study medication if the action taken with study medication is recorded on the CRF as 'study medication stopped'.

An AE will be considered fatal if the outcome is recorded on the CRF as 'patient died'.

The following summaries will be generated:

- Overall summary of AEs, including number of patients reporting each of; TEAEs, treatment related TEAEs, TEAEs leading to withdrawal, treatment related TEAEs leading to withdrawal, serious TEAEs, treatment related serious TEAEs.
- Summary of TEAEs.
- Summary of treatment-related TEAEs.
- Summary of TEAEs by maximal severity.
- Summary of TEAEs by sex.
- Summary of serious TEAEs.
- Summary of treatment-related serious TEAEs.
- Summary of TEAEs leading to permanent discontinuation of study medication.

- Summary of treatment-related TEAEs leading to permanent discontinuation of study medication.
- Summary of fatal TEAEs.
- Summary of TEAEs by time of first onset of AE.
- Summary of TEAEs by time to AE resolution.
- List of patients experiencing TEAEs by SOC and preferred term.

For the summary of TEAEs by maximal severity, for each patient, the worst severity recorded by preferred term, SOC and overall will be used for summary purposes. If severity is missing, the worst case (severe) will be assumed.

For the summary of TEAEs by time of first onset of AE, data will be summarized under the following categories:

- Weeks 1 to 2 (Day 1 to 14).

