- Weeks 3 to 6 (Day 15 to 42).
- Weeks 7 to 10 (Day 43 to 70).
- Weeks 11 to 14 (Day 71 to 98).
- >14 weeks (> Day 98).

The time to first onset of AE will be calculated for TEAEs as:

$$\text{Start date of AE} - \text{Date of first dose of OLE IMP} + 1$$

If patients have multiple occurrences of an AE then the AE will be counted once for the first occurrence only. Percentages will be based on the number of patients in the safety analysis set who have a visit or follow-up call within each time period above.

For the summary of TEAEs by time to AE resolution, data will be summarized under the following categories:

- 1 week (≤ 7 days).
- 2 weeks (8 to 14 days).
- 3 weeks (15 to 21 days).
- 4 weeks (22 to 28 days).
- >4 weeks (>28 days).
- Ongoing (for AEs not resolved).

The time to AE resolution will be calculated for TEAEs as:

$$\text{Stop date of AE} - \text{Start date of AE} + 1$$

If patients have multiple occurrences of an AE then the AE will be counted once for the occurrence with the longest time to AE resolution. However, if any of the AEs are not resolved, then the AE will be counted once within the 'Ongoing' category.

For time of first onset of AE and time to AE resolution, partial or missing dates will be handled according to Section 4.1.2.2. If an AE has a partial start date and it is unclear from the partial date (or the stop date) whether the AE started prior to or post first dose of IMP then the start date will be imputed as the date of first dose of IMP in the OLE (Day 1). The start and stop day of the AE relative to the first dose of IMP (as recorded on the CRF) will be calculated as per Section 4.1.3. For partial dates, if it is clear from the partial date that

the start/stop day was prior to the first dose of IMP, then 'pre' will be listed, similarly if it is clear that the event was post the first dose of IMP then 'post' will be listed as the start/stop day as appropriate.

All AEs will be listed. Listings will include the start and stop day of the AE, a flag for treatment emergence, and limited demographic information about the patient (age, sex, race and weight at screening). A separate listing will be provided for pre-treatment AEs, serious AEs and events of special interest (see [Appendix 1](#)).

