4.5.8.13 Exposure to Study Medication

Patients are required to take IMP twice daily (morning and evening). The first OLE dose will be taken in the clinic on Visit 1 (Day 1). The date of final dose in the study will be recorded on the CRF. The date of final dose, for patients who enter the taper period, will be recorded on the CRF at the end of taper visit.

The total number of dosing days in the study will be calculated as:

$$(\text{Date of last dose in the treatment phase} - \text{Date of Day 1}) + 1$$

The date of last dose in the treatment phase will be obtained from the CRF at the end of treatment visit.

The total number of dosing days in the study will be summarized for all patients, and patients who completed the treatment phase. The modal dose will be calculated for each patient over the same periods associated with IVRS calls for seizure reporting and will subsequently be summarized. Furthermore, a categorical summary of patients whose largest dose was 20 mg/kg/day or less, patients whose largest dose was over 20 mg/kg/day and less than 30 mg/kg/day, and patients whose largest dose was 30 mg/kg/day or more during the OLE study will be presented.

The above summaries will be repeated for the following subgroups:

- Excluding data for patients from study GWEP1332 Part A
- Patients taking clobazam
- Patients not taking clobazam
- Core study actual treatment: GWP42003-P
- Core study actual treatment: Placebo
- Patients taking clobazam; core study actual treatment: GWP42003-P
- Patients not taking clobazam; core study actual treatment: GWP42003-P
- Patients taking clobazam; core study actual treatment: Placebo
- Patients not taking clobazam; core study actual treatment: Placebo

The modal dose for each patient will be calculated across their entire period of exposure, and the number of patients and patient-years exposure will be summarized in the following groups:

- $\leq 20\text{mg/kg/day}$
- $20 - < 25\text{mg/kg/day}$
- $\geq 25\text{mg/kg/day}$

For each group, the total number of patient-years of exposure will be calculated as the sum of the total number of dosing days for each patient divided by 365.25. For the calculation of modal dose, patients will be assumed to be taking 20 mg/kg/day unless a dose adjustment is recorded.

Any missed doses during treatment should be recorded on the 'IMP Missed Doses Log' CRF page.

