Table Number	Title	Analysis Set
Table 9.17.2.4	Summary of Cognitive Assessment Battery Parent Measures - Behavior Report Form	Safety Analysis Set
Table 10.1	Summary of Exposure	Safety Analysis Set
Table 10.2	Summary of Exposure - Excluding Study GWEP1332 Part A	Safety Analysis Set
Table 10.3.1	Summary of Exposure - Patients Taking Clobazam	Safety Analysis Set
Table 10.3.2	Summary of Exposure - Patients Not Taking Clobazam	Safety Analysis Set
Table 10.4.1	Summary of Exposure - Core Study Actual Treatment of Placebo	Safety Analysis Set
Table 10.4.2	Summary of Exposure - Core Study Actual Treatment of Active	Safety Analysis Set
Table 10.5.1	Summary of Exposure - Core Study Actual Treatment of Placebo and Taking Clobazam	Safety Analysis Set
Table 10.5.2	Summary of Exposure - Core Study Actual Treatment of Placebo and Not Taking Clobazam	Safety Analysis Set
Table 10.5.3	Summary of Exposure - Core Study Actual Treatment of Active and Taking Clobazam	Safety Analysis Set
Table 10.5.4	Summary of Exposure - Core Study Actual Treatment of Active and Not Taking Clobazam	Safety Analysis Set
Table 10.6	Summary of Patient-years (On Treatment) by Modal Dose Group	Safety Analysis Set
Table 11.1	Overall Summary of Treatment Emergent Adverse Events	Safety Analysis Set
Table 11.2	Summary of Treatment Emergent Adverse Events	Safety Analysis Set
Table 11.3	Summary of Treatment-Related Treatment Emergent Adverse Events	Safety Analysis Set
Table 11.4	Summary of Treatment Emergent Adverse Events by Maximal Severity	Safety Analysis Set
Table 11.5	Summary of Treatment Emergent Adverse Events by Sex	Safety Analysis Set
Table 11.6	Summary of TEAEs by Time of First Onset of AE	Safety Analysis Set
Table 11.7	Summary of TEAEs by Time to AE Resolution	Safety Analysis Set
Table 11.8	List of Patients Experiencing Treatment Emergent Adverse Events by System Organ Class and Preferred term	Safety Analysis Set
Table 12.1	Summary of Serious Treatment Emergent Adverse Events	Safety Analysis Set
Table 12.2	Summary of Treatment-Related Serious Treatment Emergent Adverse Events	Safety Analysis Set
Table 12.3	Summary of Treatment Emergent Adverse Events Leading to Permanent Discontinuation of Study Medication	Safety Analysis Set
Table 12.4	Summary of Treatment-Related Treatment Emergent Adverse Events Leading to Permanent Discontinuation of Study Medication	Safety Analysis Set

Table Number	Title	Analysis Set
Table 12.5	Summary of Fatal Treatment Emergent Adverse Events	Safety Analysis Set

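### No adverse event table is split by Core Study treatment, so the pooled percentages, above all for Weeks 1–2, can understate incidence at first exposure if experienced patients have lower incidence

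*SAP*

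**What the plan says.** The AE profile leads the primary endpoint (Protocol 4.1.1, SAP 3.3.1). For all endpoints SAP 4.5.1 states: "Endpoints will be summarized by indication including an appropriate overall summary, unless specified otherwise". In SAP 4.5.2 the only further split by a patient characteristic is "Summary of TEAEs by sex". The severity, onset and resolution tables classify the event, not the patient's history. No title among Tables 11.1–11.8 and 12.1–12.5 in SAP Appendix 5 mentions Core treatment.

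Time of onset (Table 11.6) is counted for everyone from the "Date of first dose of OLE IMP". Its windows are Weeks 1–2, 3–6, 7–10 and 11–14, then one open category beyond Week 14.

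The same SAP does use Core treatment elsewhere. SAP 4.5.8.13 lists the subgroup "Core study actual treatment: Placebo", and Table 10.4.1 is titled "Summary of Exposure - Core Study Actual Treatment of Placebo". SAP 4.5.9 and Tables 9.5.1.1–9.5.6.4 do likewise for seizures. Neither document says why AEs are left out.

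Two rules shape who arrives and what is counted:

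- Protocol 6.1 requires that the "Patient has completed the treatment phase of their Core Study".
- Protocol 9.1.14 and 13.6.2.1 treat an AE continuing from the Core Study as treatment emergent only if it worsens. SAP 4.5.2 defines treatment emergence by a start date on or after the first extension dose.

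**The concern.** The two groups enter in different states. Core-placebo patients meet the product for the first time on Day 1. Core-active patients have been exposed already, for 14 weeks in the Phase III studies and 21 days in GWEP1332 Part A, and anyone who stopped Core treatment early is not among them. An AE that began on active drug in the Core Study and simply persists is not counted, whereas the same AE in a Core-placebo patient starting the drug is.

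The first two weeks also differ in kind. Under Protocol 9.2.1, patients without a dosing gap take their last Core dose on the morning of Visit 1 and start titration that evening. Appendix 4 then gives 2.50 mg/kg in total on Day 2 and reaches 20 mg/kg/day on Day 11. For a Core-placebo patient this is initiation. For a patient coming without a gap from 20 mg/kg/day it begins with a fall in dose. A single Weeks 1–2 column combines the two.

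At stake is how the AE percentages are read. Someone who wants the incidence to expect on starting the product may take it from a column in which most patients are not starting it.

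**Working it through.** The plan has no figure to reproduce. The target of about 680 patients has no formal calculation, and no AE rate is given. The check is therefore the size of the mixture and what it does over a range of assumed rates.

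**Step 1: share of Core-placebo patients.** Numbers randomised and ratios are from SAP Table 1, reading 4:1 in Part A as active to placebo.

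| Core study | Randomised | Placebo fraction | Placebo |
|---|---|---|---|
| GWEP1332 Part A | 34 | 1/5 | 6.8 |
| GWEP1332 Part B | 120 | 1/2 | 60.0 |
| GWEP1424 | 199 | 1/3 | 66.3 |
| GWEP1423 | 171 | 1/2 | 85.5 |
| GWEP1414 | 225 | 1/3 | 75.0 |
| Total | 749 | | 293.6 |

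w = 293.6/749 = 39.2% placebo, leaving 455.4 (60.8%) active. By indication, w is 133.1/353 = 37.7% in DS and 160.5/396 = 40.5% in LGS.

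Roll-over by arm is not given. With 680 entrants, 749 − 680 = 69 do not roll over. If all 69 were placebo patients, w = (293.6 − 69)/680 = 33.0%. If all were active patients, w = 293.6/680 = 43.2%.

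**Step 2: effect of pooling.** Let pN be incidence in IMP-naive patients, pE in experienced patients, and R = pE/pN. Then pooled incidence = w·pN + (1 − w)·pE, and pooled/naive = w + (1 − w)·R. R is assumed over a range, because the documents give no rates.

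| R | Pooled/naive at w = 0.392 |
|---|---|
| 0.25 | 0.54 |
| 0.5 | 0.70 |
| 0.75 | 0.85 |
| 1 | 1.00 |
| 1.25 | 1.15 |

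At R = 0.5 the ratio runs only from 0.67 to 0.72 as w moves from 0.33 to 0.43, so R matters far more than roll-over. As an example, 30% naive and 15% experienced in Weeks 1–2 pool to 0.392 × 30 + 0.608 × 15 = 20.9%.

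**Step 3: cumulative tables.** Keep 30% and 15% early, and add the same later risk L in both groups, so that cumulative incidence is 1 − (1 − p)(1 − L).

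| L | Naive | Experienced | Pooled | Pooled/naive |
|---|---|---|---|---|
| 0.2 | 44.0% | 32.0% | 36.7% | 0.83 |
| 0.5 | 65.0% | 57.5% | 60.4% | 0.93 |
| 0.8 | 86.0% | 83.0% | 84.2% | 0.98 |

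The gap is largest in the early columns of Table 11.6 and for early one-off events. It is small for common events over long follow-up.

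**Step 4: precision after a split.** 680 × 0.392 ≈ 267 IMP-naive and 413 experienced patients. At 20% incidence the 95% half-width is 1.96·√(0.2 × 0.8/267) = ±4.8 points, against ±3.0 for 680. The rule-of-three bound for an event never seen is 3/267 = 1.1%, against 3/680 = 0.44%.

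**The case against.** The stated objective is long-term safety and tolerability in the extension population, with descriptive summaries only. The pooled table answers that, and it serves rare events better. Neither document plans a statement about new users. This stands, and it is why the pooled tables should remain.

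The groups are also less distinct than the labels suggest:

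- About 141 of the 455 active patients (199/3 + 225/3) were randomised to 10 mg/kg, and some in Part A to 5 or 10 mg/kg. SAP 3.1.1 says "Upon entering this study, patients will titrate to 20 mg/kg/day", and Protocol 8.1.2 gives 10–20 mg/kg/day as the target. Many ex-active patients therefore had not tolerated the doses that they may reach here.
- Everyone re-titrates. Entry from the Core taper or after a gap is allowed, so the dose fall applies to only some patients.
- Any event starting after the first extension dose counts, including a recurrence. A worsened pre-treatment event gets a new record (Protocol 12.5).
- IMP-naive is the accurate term: Protocol 6.2 excludes cannabis use only within the previous 3 months.

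These points narrow the likely contrast and could reverse it for some events, but they do not show that it is absent.

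A further reply is that the split can be recovered. Under SAP 4.3 all listings are sorted by Core treatment, and the AE listings carry start day and a treatment-emergence flag. The two kinds of early event are thus not indistinguishable; they are untabulated. Counting by hand across about 680 patients is not a practical substitute.

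**Conclusion.** The point holds in conditional form. The AE tables pool about 39% first-exposed with about 61% previously exposed patients, and the split that the SAP makes for exposure and seizures is missing for AEs. Selection of Core completers and the counting rule for ongoing events both make lower incidence in experienced patients plausible. If it is lower, pooled percentages understate incidence at first exposure: by about 30% at R = 0.5 in an early window, and by 2% to 17% in the cumulative examples above.

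A reader might infer that the primary AE profile is biased in the drug's favour, or that it describes no real group. The documents support neither. They give no rates by prior exposure, the gap is zero at R = 1 and changes sign above it, and the pooled column does describe the extension population. The sizes rest on assumed values of R, equal roll-over by arm for w = 0.392, and equal later risk in Step 3. Only the split would show whether pooling misleads for a given event. This is a cheap improvement, not a defect that undermines the primary summary.

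**What to change.** Keep the pooled tables. Add to SAP 4.5.2: Tables 11.1–11.4, 11.6 and 12.1–12.5 will be repeated by Core study actual treatment (GWP42003-P, Placebo), and any statement on AE incidence at first exposure will rest on the Core-placebo columns. If output must be limited, Table 11.6 comes first.

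Do not add a version with onset timed from the first-ever dose. Phase III ex-active patients bring 14 weeks (98 days) of Core treatment, so nearly all their extension onsets would fall in the open category beyond Day 98. That display would tell the reader little unless Core Study AEs were merged in, which is a different analysis.

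The cost is SAP wording and repeat tables on a variable already used as a subgroup and listing key, with no new data and no protocol amendment. The downside is more output and smaller denominators: about 267 IMP-naive patients, or ±4.8 points at 20% incidence against ±3.0 pooled.

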4.5.2 Adverse Events

All reported AEs will be classified by system organ class (SOC), preferred term and lower level term using Version 17.1 of MedDRA.

Summaries will be presented by SOC and preferred term.

A treatment emergent AE (TEAE) is defined as an AE with a start date on or after the first dose of IMP within this OLE study. If an AE has a partial start date and it is unclear from the partial date (or the stop date) whether the AE started prior to or post first dose of IMP then the AE will be considered treatment emergent. If the start date of the AE is the same as the date of first dose of IMP and the plausible relationship to study medication is marked on the CRF as "Prior to study medication" then the AE will not be considered treatment emergent.

An AE will be considered treatment-related if the plausibility relationship to study medication is recorded on the CRF as 'yes'. If the data on plausibility relationship to study medication is missing then the AE will be considered treatment-related.

An AE will be considered leading to permanent discontinuation of study medication if the action taken with study medication is recorded on the CRF as 'study medication stopped'.

An AE will be considered fatal if the outcome is recorded on the CRF as 'patient died'.

The following summaries will be generated:

- Overall summary of AEs, including number of patients reporting each of; TEAEs, treatment related TEAEs, TEAEs leading to withdrawal, treatment related TEAEs leading to withdrawal, serious TEAEs, treatment related serious TEAEs.
- Summary of TEAEs.
- Summary of treatment-related TEAEs.
- Summary of TEAEs by maximal severity.
- Summary of TEAEs by sex.
- Summary of serious TEAEs.
- Summary of treatment-related serious TEAEs.
- Summary of TEAEs leading to permanent discontinuation of study medication.

- Summary of treatment-related TEAEs leading to permanent discontinuation of study medication.
- Summary of fatal TEAEs.
- Summary of TEAEs by time of first onset of AE.
- Summary of TEAEs by time to AE resolution.
- List of patients experiencing TEAEs by SOC and preferred term.

For the summary of TEAEs by maximal severity, for each patient, the worst severity recorded by preferred term, SOC and overall will be used for summary purposes. If severity is missing, the worst case (severe) will be assumed.

For the summary of TEAEs by time of first onset of AE, data will be summarized under the following categories:

- Weeks 1 to 2 (Day 1 to 14).
- Weeks 3 to 6 (Day 15 to 42).
- Weeks 7 to 10 (Day 43 to 70).
- Weeks 11 to 14 (Day 71 to 98).
- >14 weeks (> Day 98).

The time to first onset of AE will be calculated for TEAEs as:

$$\text{Start date of AE} - \text{Date of first dose of OLE IMP} + 1$$

If patients have multiple occurrences of an AE then the AE will be counted once for the first occurrence only. Percentages will be based on the number of patients in the safety analysis set who have a visit or follow-up call within each time period above.

For the summary of TEAEs by time to AE resolution, data will be summarized under the following categories:

- 1 week (≤ 7 days).
- 2 weeks (8 to 14 days).
- 3 weeks (15 to 21 days).
- 4 weeks (22 to 28 days).
- >4 weeks (>28 days).
- Ongoing (for AEs not resolved).

The time to AE resolution will be calculated for TEAEs as:

$$\text{Stop date of AE} - \text{Start date of AE} + 1$$

If patients have multiple occurrences of an AE then the AE will be counted once for the occurrence with the longest time to AE resolution. However, if any of the AEs are not resolved, then the AE will be counted once within the 'Ongoing' category.

For time of first onset of AE and time to AE resolution, partial or missing dates will be handled according to Section 4.1.2.2. If an AE has a partial start date and it is unclear from the partial date (or the stop date) whether the AE started prior to or post first dose of IMP then the start date will be imputed as the date of first dose of IMP in the OLE (Day 1). The start and stop day of the AE relative to the first dose of IMP (as recorded on the CRF) will be calculated as per Section 4.1.3. For partial dates, if it is clear from the partial date that

the start/stop day was prior to the first dose of IMP, then 'pre' will be listed, similarly if it is clear that the event was post the first dose of IMP then 'post' will be listed as the start/stop day as appropriate.

All AEs will be listed. Listings will include the start and stop day of the AE, a flag for treatment emergence, and limited demographic information about the patient (age, sex, race and weight at screening). A separate listing will be provided for pre-treatment AEs, serious AEs and events of special interest (see [Appendix 1](#)).

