9.1.14 Adverse Events

Any adverse changes in the patient’s medical condition, following completion of the consent/assent form by the patient, will be recorded on the CRF as AEs, questioning the patient further if necessary. Any AEs that are continuing from the Core Study will be carried over into the OLE study and transcribed in the CRF, only becoming classified as treatment emergent if they worsen. All AEs occurring during the study, whether or not attributed to the IMP, observed by the Investigator or reported by the patient will be recorded in the CRF.

SAEs must be reported to GW Pharmacovigilance Department (PVD) within 24 hours of discovery or notification of the event, and recorded in the CRF.

Refer to [Section 12](#) for definitions, procedures and further information.

The number of inpatient hospitalizations that are, in the Investigator's opinion, due to epilepsy will be recorded in the patient's CRF and through the SAE reporting process.

Refer to [Section 9.1.15.1.1](#) for the list of 'Triggering AEs of Interest' associated with monitoring of drug abuse liability.

9.1.15 Monitoring of Drug Abuse Liability (for Patients 12 Years of Age and Older)

There are 2 triggers that will require the Investigator or study coordinator to discuss abuse potential signals with the patient or their caregiver. These are either AEs of interest that may be reported by the patient/caregiver, or drug accountability issues regarding overuse of the IMP or missing bottles. Different questionnaires will be completed by the site depending upon which trigger occurs (see [Figure 9-1](#)).

Irrespective of the above, all patients/caregivers will be interviewed at their final dosing visit ('End of Treatment'/Withdrawal visit or 'End of Taper Period' visit, as applicable) and a Study Medication Use and Behavior Survey will be completed by the Investigator or study coordinator. Investigators and study coordinators will be provided with training on how to complete and perform the processes outlined in this section. This training must be completed and documented by the relevant site staff prior to implementation at site.

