12.5 Causality Assessment

Causality assessment is required for all AEs and SAEs. Causality assessment must only be assigned by the Investigator. All cases judged as having a reasonable suspected causal relationship to the IMP must be reported as such. The expression "*reasonable causal relationship*" is meant to convey in general that there are facts (evidence) or arguments to suggest a causal relationship.

The following question which must be answered by the Investigator for all AEs is used to capture the reasonable causal relationship of an event to the IMP:

"In your opinion is there a plausible relationship to the IMP?" The answer is "yes", or "no".

Where a pre-treatment event worsens in severity following the first dose of IMP a new event record should be entered into the CRF.

Considering the explanation given above, Investigators are strongly encouraged to express their opinion on what the cause of an AE might be. For individual patients, the Investigator is usually in the best position to assess the underlying suspected cause of an AE. For all AEs and especially SAEs, it is important that the Investigator assess not only the possible role of the IMP but also competing etiological factors as the underlying cause. Factors for consideration may include:

- Medical and disease history.
- Lack of efficacy/worsening of treated condition.
- Concomitant or previous treatment.
- Withdrawal of IMP.
- Protocol-related procedure.

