If the severity of an AE fluctuates day-to-day, for example, a headache or constipation, the change in severity should not be recorded each time, instead only the worst observed severity should be recorded with AE start and stop dates relating to the overall event duration regardless of severity.

A severe AE is not the same as a SAE. For example, a patient may have severe vomiting but the event does not result in any of the SAE criteria above. Therefore it should not be classed as serious.

E) Causality

See [Section 12.5](#) above.

F) Action Taken with Study Medication

This question refers to the action taken with the IMP due to an AE. The action with the IMP must be classed as:

- None.
- Dose reduced temporarily.
- Dose reduced.
- Study medication interrupted.
- Study medication stopped.

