13.6.2.1 Adverse Events

AEs will be coded according to the Medical Dictionary for Regulatory Activities dictionary.

A treatment emergent AE is one that started, worsened in severity or seriousness, following the first dose of IMP in this study. Any AEs that are continuing from the Core Study will be carried over into the OLE study and transcribed in the CRF, only becoming classified as treatment emergent if they worsen.

Descriptive presentations of treatment emergent AEs will be given by preferred term and system organ class for the safety analysis set. The number of patients reporting at least one AE will be provided.

The following summaries will be produced:

- Pre-existing AEs.
- All-causality AEs.
- Treatment related AEs.
- All-causality AEs by severity.
- All-causality serious AEs.
- Treatment related serious AEs.
- AEs reported as leading to permanent cessation of study treatment.
- Fatal AEs.

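### SAP 4.5.2 defines treatment-emergent AEs by start date alone and drops the protocol's worsening limb undeclared, leaving a gap for carried-over AEs that become serious or fatal

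*SAP*

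**What the plan says.** Protocol 13.6.2.1 gives two routes to treatment emergence: "A treatment emergent AE is one that started, worsened in severity or seriousness, following the first dose of IMP in this study". For patients rolling over, Protocol 9.1.14 adds: "Any AEs that are continuing from the Core Study will be carried over into the OLE study and transcribed in the CRF", with such events "only becoming classified as treatment emergent if they worsen".

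SAP 4.5.2 keeps one route. A TEAE "is defined as an AE with a start date on or after the first dose of IMP within this OLE study". Where a partial date leaves it unclear "whether the AE started prior to or post first dose of IMP then the AE will be considered treatment emergent". That convention leans towards counting, but it still concerns onset only.

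SAP 4.7 lists the endpoints left out and the change to medical history. It does not mention the TEAE definition.

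**The concern.** The AE profile leads the primary endpoint (Protocol 13.6.2, SAP 3.3.1), and the TEAE definition decides which events enter its tables. Every AE summary listed in SAP 4.5.2 and in Appendix 5 (Tables 11.1 to 12.5) is a TEAE summary. The protocol also planned a summary of pre-existing AEs; the SAP has only a listing (Listing 11.2). An event that fails the start-date test therefore appears in no AE summary table.

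All patients come from a Core Study, and entry on the same day or during the Core Study taper is encouraged, so AEs ongoing at the first OLE dose are to be expected. Doses may also be raised during maintenance. Worsening of an existing event is thus one of the long-term signals the study should be able to show.

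**Working it through.** There is no sample size formula, test or stated figure to reproduce, so the check sets the definitions beside the recording rules that decide which start date an event carries.

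**Inputs**

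- Protocol definition: new onset, or worsening in severity or seriousness (13.6.2.1; the carried-over case again in 9.1.14).
- SAP definition: start date only (4.5.2).
- Recording rule for worsening, Protocol 12.5: "Where a pre-treatment event worsens in severity following the first dose of IMP a new event record should be entered into the CRF".
- Recording rule for severity that varies from day to day, Protocol 12.6 D: "only the worst observed severity should be recorded with AE start and stop dates relating to the overall event duration regardless of severity".
- Assumption: a transcribed Core Study AE keeps its original onset date. The documents do not say so, but it is the natural reading of transcription.

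**Outcome for a carried-over AE after the first OLE dose**

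| What happens | Protocol 13.6.2.1 | Recording rule | SAP 4.5.2 |
|---|---|---|---|
| Unchanged | Not a TEAE | Transcribed record only | Not a TEAE |
| Severity rises; new record dated at the worsening | TEAE | 12.5 | TEAE |
| Severity rises; new record given the original onset date, or old record merely updated | TEAE | 12.5 silent on the date, or not followed | Missed |
| Becomes serious or fatal at the same severity grade | TEAE | No new-record rule | Missed |

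The second row is where the two definitions agree in practice. The third depends on site behaviour. The wording of 12.5 leaves room for it: besides giving no start date for the new record, it speaks of a pre-treatment event and a first dose without saying whether these mean the OLE or the Core Study. For a patient who received active drug in the Core Study, a Core Study AE is not clearly pre-treatment.

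The fourth row follows from the text itself. Protocol 12.6 D separates severity from seriousness, and under 12.2 inpatient hospitalization is enough to make an AE serious. Rule 12.5 is triggered by severity alone. For deaths, SAP 4.5.2 goes by the recorded outcome, and Protocol 12.1.1 wants the underlying cause as the event term. If that cause was already ongoing at rollover and its record is updated rather than replaced, the death does not reach the fatal TEAE table.

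**Direction.** Removing one of two qualifying routes leaves a subset of the events, so the counts fall or stay the same.

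**Scale only.** With planned enrolment of about 680, each 1% of patients whose only qualifying event is missed is 680 × 0.01 = 6.8, about 7 patients. An assumed 0.5% to 5% gives 680 × 0.005 = 3.4 to 680 × 0.05 = 34 patients. These percentages are assumptions; nothing in the documents anchors them.

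**The case against.** The best defence is that data capture does the work the SAP sentence omits. Protocol 12.5 asks for a new record when severity increases. Protocol 12.1.1 includes worsening of an existing condition in the definition of an AE, and 12.6 requires worsening seizures to be documented as AEs. A worsening entered as its own record, dated when it happened, meets the SAP rule. Events that are still missed are not hidden: SAP 4.5.2 lists all AEs with a treatment-emergence flag and gives separate listings for pre-treatment and serious AEs. The primary endpoint also covers laboratory, ECG, vital-sign and other safety data.

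Much of this stands. A reader might infer that every worsened carried-over AE drops out of the primary endpoint, or out of every AE table. The documents do not support that, because 12.5 should bring many severity worsenings back in. A reader might also take 12.6 D as telling sites to keep a single record for any worsening. It does not: it applies only to day-to-day fluctuation, and a sustained worsening belongs under 12.5. A site could misapply it, but that is a conduct risk.

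The defence does not close the gap for seriousness, does not settle the start date of the new record, and does not explain why the two definitions differ. Listings show individual events; they do not restore them to the summary counts.

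**Conclusion.** The SAP's TEAE definition is narrower than the protocol's, and the change is undeclared. The clear loss is a carried-over AE that becomes serious or fatal without a higher severity grade. Severity worsenings that are not re-recorded, or not dated at the worsening, are a further possible loss. The affected outputs are the TEAE, serious TEAE and fatal TEAE summaries. The effect runs one way, towards lower counts.

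Its size cannot be estimated. A reader might multiply assumed rates, for example 30% to 60% of patients with an ongoing AE and 5% to 20% of those worsening: 680 × 0.30 × 0.05 = 10.2 to 680 × 0.60 × 0.20 = 81.6 patients. That range should not be used. Neither rate is in the documents, and the product includes the events that 12.5 already captures. A patient also leaves the overall TEAE count only if no other event of theirs qualifies.

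The contradiction in wording is certain. Its consequence rests on transcribed records keeping their original start date and on how sites apply 12.5.

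**What to change.** In SAP 4.5.2, define a TEAE as an AE that starts on or after the first OLE dose, or an AE ongoing at the first OLE dose whose severity or seriousness increases afterwards. Then add three rules:

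1. **Dating.** For the second group, use the date of worsening as onset in the time-to-onset and time-to-resolution tables. Otherwise these events would carry onset days before the first OLE dose and inflated durations.
2. **Data check.** Compare carried-over OLE records with the matching Core Study records where these are available, for both severity and seriousness. The Core Study CRFs are not among the documents. If those studies also stored only the worst severity of a fluctuating event, severity at Core Study exit may not be recoverable.
3. **Single counting.** Where a new record under Protocol 12.5 already exists, count the event once and do not also reclassify the transcribed record.

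The cost is a short SAP edit, one data check or merge, and slightly higher TEAE counts.
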